3.2.5 Brain and/or Spine MRI

All patients must have a brain MRI with and without contrast (gadolinium) within **30 days** prior to study enrollment. All patients with history of spinal or leptomeningeal disease and those patients with symptoms suspicious of spinal disease, must have a spine MRI with contrast (gadolinium) performed within **30 days** prior to study enrollment. Lumbar Puncture is necessary if there is evidence of tumor dissemination on the MRI of spine.

3.2.6 Performance status

Performance Level: Karnofsky >or equal to 50% for patients > 10 years of age or Lansky > or equal to 50 for patients < 10 years of age (Appendix I). Note: Patients who are unable to walk because of paralysis, but who are up in a wheelchair, will be considered ambulatory for the purpose of assessing the performance score.

3.2.7 Prior therapy

- 3.2.7.1 No limit in the number of previous surgical resections.
- 3.2.7.2 No limit to number of prior anti-cancer regimens, including chemotherapy, biologic agents, immunotherapy, vaccines, monoclonal antibodies or radiation therapy. Patients who have received prior radiation therapy for this tumor are eligible. There should be at least 2 yearstime since the completion of radiation therapy.

3.2.8

Patients must have recovered (to CTC v.5.0 ≤ Grade 1 unless indicated below) from the acute toxic effects of all prior chemotherapy, immunotherapy prior to entering this study, with the exception of alopecia, weight changes and Grade I or II lymphopenia.

a -Myelosuppressive chemotherapy: Must not have received within 3 weeks of enrollment onto this study (6 weeks if prior nitrosourea).

B -Biologic (anti-neoplastic agent): At least 7 days must have elapsed since the completion of therapy with other biologic agents. For other biologic agents that have known adverse events occurring beyond 7 days after administration, this period must be extended beyond the time during which adverse events are known to occur. **The duration of this interval must be discussed with the study chair.**

c -Monoclonal antibodies: At least 3 half-lives of the antibody after the last dose of a monoclonal antibody. Specifically for bevacizumab 36 days after the last dose.

d -Resection: At least 3 weeks from the last surgical resection, prior to start study drug.

e -Immunotherapy: At least 42 days after the completion of any type of immunotherapy, e.g. tumor vaccines.

g - Radiation therapy (RT): Patients must have had their last fraction of cranial or craniospinal Radiation ≥ 24 months prior to study entry.

f. Study specific limitations on prior therapy:

1) Patients who have received Poly-ICLC are eligible for this trial if all acute Poly-ICLC -related toxicity has resolved.

2) Patients must not have received Pegylated interferon previously.

3.2.9 Concomitant Medications Restrictions

- a. Growth factor(s): Must not have received within 2 weeks of entry onto this study.
- b. Steroids: Patients who are receiving corticosteroids must be on a stable or decreasing dose for at least 1 week prior enrollment in the study.

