4.1 Overview of the treatment plan

Treatment with pegylated interferon alpha-2b must begin within 14 days of patient enrollment. Patients may be pre-medicated as needed with acetaminophen 10-15 mg/kg (maximum 650 mg per dose) or ibuprofen 10 mg/kg within 1 hour of receiving Pegylated interferon. The patients can continue on either acetaminophen or ibuprofen for up to 48 hours after Pegylated interferon injection. The maximum dose of ibuprofen in a 24-hour period will be 40 mg/kg. Ibuprofen for Adolescents and Adults the maximum daily dose: 2.4 grams in 24 hours. Premedication is optional.

Each cycle of therapy will consist of pegylated interferon alfa-2b administered subcutaneously once weekly (**+/- 5days**) for 4 weeks for up to 2 years. Each dose should be administered on the same day

each week. There will be no breaks between cycles. Total number of cycles 26. Each dose is 1µg/kg subcutaneously. Nursing staff will instruct the patients or their caregivers regarding sites of injection and injection technique. Teaching needs to be documented. Rotating the sites of injection is strongly recommended.

Patients and/or their caregivers will be asked to maintain a diary (Appendix 5) documenting the dose of pegylated interferon alpha-2b given, site of administration and any side effects. This diary will be reviewed at each clinic visit. Patients will return to the Aflac clinic prior to start next cycles.

Doses could be rounded up to the nearest upper 5mcg for easier administration. For patients whose weight is greater than 150kg the maximum dose of Pegylated interferon to be administered is 150mcg/dose/ week.

MRI brain and /or spine will be performed as a baseline within **30 days** of enrollment and subsequently every 3 cycles.

See section 7.1 for required observations prior to start therapy.

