4.2 Concomitant therapy restrictions

4.2.1

Concurrent cancer therapy, including chemotherapy, radiation therapy, immunotherapy, or biologic therapy can **NOT** be administered to patients while on this study. The use of alternative or complementary therapies is discouraged.

4.2.2

Radiotherapy is not permitted.

4.2.3

Filgrastim (G-CSF) may be used at the treating physician's discretion in patients with severe neutropenia (i.e. ANC <500/µL) to enhance neutrophil recovery when clinically indicated (for culture proven bacteremia or invasive fungal infections). Prophylactic or routine use of filgrastim in clinically well patients awaiting count recovery is not recommended.

4.2.4

Corticosteroid therapy is permissible only for the treatment of increased intracranial pressure or physiologic replacement. The lowest dose consistent with good medical management should be used. Corticosteroids should **NOT** be used as an antiemetic due to their effect on the blood brain barrier. Patients on steroids who require an increase in steroid dose for worsening neurologic symptoms should have an MRI performed within **5 days** to rule out tumor progression.

4.2.5

Appropriate antibiotics, blood products, anti-emetics, fluids, electrolytes and general supportive care are to be used as necessary. PCP prophylaxis is recommended following the institutional guidelines when absolute lymphocyte count is below 1200.

4.2.6

Anticonvulsants may be administered as clinically indicated. However, it is recommended to avoid enzyme inducing anticonvulsants.

For Supportive Care Guidelines use Children's Oncology group guidelines, see: https://members.childrensoncologygroup.org/prot/reference_materials.asp under Standard Sections for Protocols.

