10.3 Tumor measurement

Given the complexity of JPA/ OPG, the tumor size/response will be assessed in different segments:

1. Optic nerve (right, left)

2. Chiasm /hypothalamus
3. Brain parenchyma / retrochiasmatic visual pathways (optic tracts, optic radiations, internal capsule, posterior fossa) (right/left).

Therefore, up to 5 measurements may be necessary.

1. Longest diameter of target lesion(s) measured from the axial plane or the plane in which the aspect of the tumor is best seen or measured, provided the same plane is used in follow ups.
2. The longest measurement of the tumor (or width, W) should be determined.
3. The perpendicular measurements (transverse (T) measurement-perpendicular to the width in the selected plane. The length (L) – tumor extent in the plane perpendicular to the selected plane will not be used for measurement purpose.
4. The lower limit of the target lesion(s) should be at least twice the thickness of the slices showing the tumor to decrease the partial volume effect (e.g. 8 mm lesion for a 4 mm slice).
5. An automated tool (OncoTreat) will be employed to evaluate how the values obtained with this tool compare with the manually derived values. The manually derived values will be the measurements used for the study.

10.4 Determination of tumor progression/response.

Progressive disease

Any patient with clinical or radiographic evidence of progressive disease following any treatment cycle will no longer receive pegylated interferon alfa-2b (see Section 5.1). Radiographic progression is defined as appearance of new tumors or an increase in any previously measurable lesion by $\geq 25\%$ in the product of the two longest perpendicular diameters or by 40% in the product of the three diameters. The preferred method for tumor measurement is to use the 3 diameters when available.

If possible, tumor progression should be documented by the appropriate radiological study. For patients who develop worsening neurological symptoms, attempts should be made to distinguish progressive disease from other causes prior to removing the patient from the study

Determination of tumor response or progression will be based on the pre-study baseline scan performed closest to time of study entry. Progressive disease will be defined based on the comparison of the baseline scan to the scan demonstrating best response.

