1. The amount of tumor enhancement is quite variable in LGGs from one scan to the next. Therefore, tumor response/progression will not solely be determined by change in the amount of enhancing disease on post contrast T1 images. Measurable change in size/extent must be present on FLAIR/T2 images, or on pre-contrast T1 images.

2. Development of new disease or progression in any established lesions is considered progressive disease, regardless of response in other lesions – e.g. when multiple lesions show opposite responses, the progressive disease takes precedence.

Note:

- CT scans should not be used to determine response. For MRI imaging, the longest diameter can be measured from the axial plane or the plane in which the tumor is best seen or measured, provided the same plane and MR sequence is used in follow ups.
- The cystic components of a tumor are considered in separate tumor measurements. See options below.

Options:

- If the cyst/necrosis is eccentric, the W, T and L of the solid portion should be measured, the cyst/necrosis excluded from measurement.
- If the cyst/necrosis is central but represents a small portion of the tumor (<25%), disregard and measure the whole lesion.
- If the cyst/necrosis is central but represents a large portion of the tumor, identify a solid aspect of the mass that can be reproducibly measured.
- Leptomeningeal tumor spread is usually not a target lesion, and usually cannot be measured accurately. Presence and location of leptomeningeal tumor spread should be noted, change in extent/thickness assessed on follow up studies.
- For patients with large cystic components (>25%): One cystic component should be identified in the baseline scan. It should be measured separately from the solid component. It should be measured in 3 dimensions in the best sequence likely the T2 sequences. (L x T x W).

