10.6 Selection of Target and Non-Target Lesions

1. For most CNS tumors, only one lesion/mass is present and therefore is considered a “target” for measurement/follow up to assess for tumor progression/response.
2. If multiple measurable lesions are present, up to 5 should be selected as “target” lesions. Target lesions should be selected on the basis of size and suitability for accurate repeated measurements. All other lesions will be followed as non-target lesions (including CSF positive for tumor cells).
3. The lower size limit of the target lesion(s) should be at least twice the thickness of the slices showing the tumor to decrease the partial volume effect (e.g. 8 mm lesion for a 4 mm slice).
4. Any change in size of non-target lesions should be noted, though does not need to be measured.

10.7 Response Criteria for Target Lesions:

Response criteria are assessed in 3 dimensions – the product of L x W x T. An elliptical model volume ($=0.5L \times W \times T$) is used.

To assess response/progression, the ratio is calculated:

$$\mathbf{L \times W \times T \text{ (current scan) / L \times W \times T \text{ (reference scan)}}$$

Development of new disease or progression in any established lesions is considered progressive disease, regardless of response in other lesions – e.g. when multiple lesions show opposite responses, the progressive disease takes precedence. Response Criteria for 3-dimensional target lesions:

Complete Response (CR): Disappearance of all target lesions.

Partial response (PR): $\geq 65\%$ decrease in the sum of the products of the three perpendicular diameters of all target lesions (up to 5), taking as reference the initial baseline measurements.

Stable Disease (SD): Neither sufficient decrease in the sum of the products of the three perpendicular diameters of all target lesions to qualify for PR (taking as reference the initial baseline measurements), nor sufficient increase in a single target lesion to qualify for PD, (taking as reference the smallest disease measurement since the treatment started).

Progressive Disease (PD): 40% or more increase in the product of perpendicular diameters of ANY target lesion, taking as reference the smallest product observed since the start of treatment, or the appearance of one or more new lesions.

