In the rare circumstance that the length of a lesion cannot be determined, then comparison of 2 dimensional measurements, T x W (product of the longest diameter and its longest perpendicular diameter) can be used.

Response Criteria for 2-dimensional target lesions:

Complete Response (CR): Disappearance of all target lesions.

Partial response (PR): ≥50% decrease in the sum of the products of the two perpendicular diameters of all target lesions (up to 5), taking as reference the initial baseline measurements.

Stable Disease (SD): Neither sufficient decrease in the sum of the products of the two perpendicular diameters of all target lesions to qualify for PR (taking as reference the initial baseline measurements), nor sufficient increase in a single target lesion to qualify for PD, (taking as reference the smallest disease measurement since the treatment started).

Progressive Disease (PD): 25% or more increase in the product of perpendicular diameters of ANY target lesion, taking as reference the smallest product observed since the start of treatment, or the appearance of one or more new lesions.

Local progression is defined as progression of known residual tumor or the appearance of tumor at known prior sites of disease that were at some point without evidence of disease. Distant progression is defined as the appearance of tumor at sites other than known prior sites of disease. Distant progression most often occurs in the subarachnoid space and may occur at any point within the neuraxis. Although rare, extra- CNS metastasis represents distant failure. Combined local and distant progression is defined when evaluation of the entire neuraxis reveals local and distant progression.

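### Steroid stability is tied to enrollment and not to the baseline MRI, and no response rule considers steroid dose, so a CR or PR scored on a higher dose than at baseline can be credited to interferon

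*Combined protocol and SAP*

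**What the plan says.** All references are to the combined protocol and SAP.

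- **Steroids at entry (3.2.9b).** "Patients who are receiving corticosteroids must be on a stable or decreasing dose for at least 1 week prior enrollment in the study". The window ends at enrollment and is not linked to any scan.
- **Baseline MRI (3.2.5).** "All patients must have a brain MRI with and without contrast (gadolinium) within 30 days prior to study enrollment".
- **Start of treatment (4.1).** "Treatment with pegylated interferon alpha-2b must begin within 14 days of patient enrollment".
- **Reference scan (10.4).** "Determination of tumor response or progression will be based on the pre-study baseline scan performed closest to time of study entry".
- **Steroids on study (4.2.4).** "Corticosteroid therapy is permissible only for the treatment of increased intracranial pressure or physiologic replacement". If the dose has to go up because neurologic symptoms worsen, an MRI is due within 5 days, to rule out progression.
- **PR (10.7).** In three dimensions, a fall of at least 65% in the "sum of the products of the three perpendicular diameters of all target lesions (up to 5), taking as reference the initial baseline measurements". In two dimensions, a fall of at least 50% in the "sum of the products of the two perpendicular diameters of all target lesions (up to 5), taking as reference the initial baseline measurements".
- **Enhancement (10.4, note 1).** A change in enhancement does not decide response or progression by itself: "Measurable change in size/extent must be present on FLAIR/T2 images, or on pre-contrast T1 images".
- **Responder (9.4).** Best overall response of CR or PR at any time on study. No confirmation scan is required.

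Sections 9.4 and 10.4 to 10.8 work from tumor dimensions, new lesions and non-target status. None mentions steroid dose. The evaluation table in 7.1 has no item for steroid dose at an MRI, and the retrospective central review in 10.9 states no steroid rule.

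**The concern.** Response is a comparison of two scans, so the conditions at the reference scan matter as much as those at the later one. The plan fixes steroid conditions for a week that may lie entirely after the reference scan. Take a patient scanned on day -30 off steroids, started on them on day -20, and stable from day -8. That patient satisfies 3.2.9b, yet the baseline is a no-steroid scan and later scans may not be. The dose can also rise on study under 4.2.4. In either case a CR or PR recorded while the dose exceeds the baseline-scan dose is counted in full.

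There is no control arm in which the same effect would appear, and the go decision turns on three patients. One misattributed response is therefore enough to matter. If the dose at each scan is not recorded, the problem could be neither detected nor corrected afterwards.

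**Working it through.** **Inputs.** Baseline MRI up to 30 days before enrollment (3.2.5). Steroid-stable period 7 days before enrollment (3.2.9b). First dose up to 14 days after enrollment (4.1). Stop if 0 of 9 respond, go if at least 3 of 17 respond, with p0 = 5% and p1 = 25% (9.2). Responder means CR or PR (9.4).

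**1. Windows.**
- Days after the reference scan that fall before the stability week: 30 - 7 = 23.
- Longest gap from reference scan to first dose: 30 + 14 = 44 days.

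**2. The plan's own design figures.**
- Probability of early termination at p0: 0.95^9 = 0.630 (plan: 0.63).
- Expected sample size: 9 × 0.630 + 17 × 0.370 = 11.96 (plan: 11.96).
- P(go | p) = sum over x = 1 to 9 of P[Bin(9, p) = x] × P[Bin(8, p) ≥ 3 - x]. This gives 0.0466 at p = 0.05 and 0.812 at p = 0.25.

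The stated design reproduces, within its 5% alpha and 80% power.

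**3. A share q of true non-responders misread as CR or PR.** The documents give no value for q, so this is an assumed range. The apparent response rate is 0.05 + 0.95q, and the same decision rule is applied.

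| q (assumed) | Apparent rate | P(go) at a true 5% |
|---|---|---|
| 0% | 0.0500 | 4.7% |
| 1% | 0.0595 | 7.1% |
| 2% | 0.0690 | 10.1% |
| 3% | 0.0785 | 13.5% |
| 5% | 0.0975 | 21.2% |
| 10% | 0.1450 | 43.3% |

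Here q is a product: the share of patients scanned on a higher dose than at baseline, times the chance that the steroid effect alone meets the PR threshold. As an illustration, if 20% were on a higher dose, q = 5% would need one in four of them to reach PR from steroids alone (0.05 / 0.20 = 0.25).

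**4. Exactly one false responder among the 17.**
- In stage 1: the stage is passed automatically, and 2 more responders are needed among the other 16. P[Bin(16, 0.05) ≥ 2] = 1 - 0.95^16 - 16 × 0.05 × 0.95^15 = 0.189.
- In stage 2: the first 9 must also yield at least one true response. Subtract P[0 of 9] × P[Bin(7, 0.05) ≥ 2] = 0.630 × 0.044 = 0.028, leaving 0.161.

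One such patient raises the false-go chance from 4.7% to between 16% and 19%.

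**The case against.** The case on the other side is substantial, and most of it limits the size of the point without removing it.

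- **Thresholds.** PR needs a 65% fall in the three-diameter product or 50% in the two-diameter product. Nothing in the documents says that steroids alone shrink these tumors that far. This stands: the text supports that such a response can count, not that it will.
- **Enhancement safeguard.** Note 1 in 10.4 blocks a response based on enhancement alone. This stands as a partial safeguard. It does not mention steroids, and a size change on FLAIR/T2 still counts.
- **Direction.** Section 3.2.9b admits a decreasing dose, and 4.2.4 asks for the lowest workable dose. A taper after baseline would bias against response. This stands, and it is a further reason to record the dose.
- **Timing.** The first response MRI comes after cycle 3, about 12 weeks into treatment, so a patient on steroids at enrollment need not still be on them. A reader might infer that every later scan is on steroids; that does not follow. Section 10.4 also uses the scan closest to entry, so a repeat scan taken after steroids began would become the reference, but no repeat is required.
- **On-study increases.** The MRI within 5 days under 4.2.4, and the removal of progressing patients, narrow this route. Neither disqualifies or adjusts a later CR or PR.
- **Purpose.** A reader might infer that 3.2.9b was written to protect the imaging endpoint and fails at it. The section gives no rationale and may simply ask for clinical stability. Nor does 4.2.4 link steroids to response scoring: it cites the blood-brain barrier only as a reason against antiemetic use.
- **Recording.** Section 12.0 defers reporting to a separate packet that is not part of the documents, so steroid dose may be captured there.

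**Conclusion.** The point holds as a gap in the definition of the primary endpoint. It is neither a contradiction nor an arithmetic error in the plan. The reference scan may precede the steroid-stable week by up to 23 days and the first dose by up to 44. Steroids may be used on study, and no response rule takes the dose into account. A CR or PR on a higher dose than at baseline is therefore credited to interferon.

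The size is unknown. The text does not support reading 21.2% or 43.3% as the trial's actual type I error: those figures rest on assumed misreading rates of 5% and 10%, and the rates of 0% to 2% give 4.7% to 10.1%. What does follow from the design is its sensitivity, since a single false responder would raise the false-go chance to 16% to 19%. These figures assume a true rate of 5%, misreading in one direction only, and CR/PR as the responder definition in 9.4. Repair is worthwhile because it is cheap and the decision rests on very few responders.

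**What to change.** Change how the endpoint is measured and scored, and place no condition on how steroids are dosed.

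1. Add to the 7.1 table the steroid dose at the baseline MRI and at each response MRI.
2. Reconcile the window in 3.2.9b with the MRI window in 3.2.5, so that the reference scan is one taken within the steroid-stable period. Repeat the baseline scan if the dose rose after it.
3. State in 10.5 and 10.7 that a CR or PR counts toward the primary endpoint only if the steroid dose at that scan is no higher than at the reference scan, physiologic replacement excepted; otherwise it is scored SD.
4. Report a sensitivity analysis that counts every CR and PR regardless of steroid dose.

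Item 3 works only if SD is not a response. The sentence in 9.2 that counts SD as response must therefore be reconciled with 1.1 and 9.4.

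The cost is a few lines of wording, one recorded field per MRI, an occasional repeat baseline scan, and a few responses classed as SD.
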